4.1 Inclusion Criteria

Patients eligible for trial must comply with all of the following at the time of randomization:

- Patients must be ≥ 2 years of age and ≤ 21 years of age
- Patients must have a confirmed diagnosis of hematologic malignancy or solid tumor malignancy
- Patients must be undergoing or planned chemotherapy or BMT
- Patients will only be eligible to receive study drug or placebo during a predicted inpatient stay of ≤ 3 days
- Patients must be predicted to have thrombocytopenia $\leq 20,000/\mu\text{L}$ for ≥ 5 days
- Patient must have a platelet transfusion threshold of $\leq 30,000/\mu\text{L}$
- Patients must be >14 days beyond their last dose of PEG-Asparaginase or >72 hours beyond their last dose of Erwinia Asparaginase (with exceptions below)

- Patients must be able to comply with treatment and monitoring

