	
 • Known inherited or acquired prothrombotic disorder • Diagnosis of DIC • WHO Grade 2 or greater bleeding within 48 hours prior to enrollment or study drug activation • Receipt of PEG-asparaginase within 7 days prior to enrollment • Receiving tranexamic acid (or other anti-fibrinolytic agent) or any other pro-coagulant agent; Receiving estrogen derivatives or progestins • Receiving therapy with anticoagulation or antiplatelet therapy • Receiving platelet growth factors • History of thromboembolic event within past six months • History of sinusoidal obstruction syndrome • Visible hematuria • Renal dysfunction (as defined in Section 6, Table 2), receiving dialysis or anuria (defined as <10mL/hr urine over 24H) • History of seizures • Known allergy to tranexamic acid • Pregnancy • Receiving outpatient therapy or predicted to have inpatient hospital stay ≤3 days • Patient with platelet count ≥30,000/uL without predicted fall in platelet count
Study type	
Interventional Allocation: randomized, 1:1 Intervention model: parallel assignment Masking: double blind (subject,

Data category	Information
	
caregiver, investigator, outcomes assessor) Primary purpose: Prevention Phase I
 
Study Period: 18 months

Date of first enrollment	TBD
Target sample size	20
Recruitment status	Pre-Recruitment
Primary outcome(s)	
Determine the feasibility of enrolling and conducting an RCT of tranexamic acid in pediatric patients with hypoproliferative thrombocytopenia
 
To define and describe safety of tranexamic acid administered on this schedule
 
To demonstrate appropriate suppression of in vitro fibrinolytic activity by tranexamic acid administered on this schedule

Key secondary outcomes	
To preliminarily define the reduction in WHO grade 2 or higher bleeding events within the confines of a Phase 1 study
 
To assess the reduction in number of platelet transfusions
 
To assess the reduction in number of red blood cell transfusions

Figure 1. Study Schematic

2. Background

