3.1 Primary Aims and Endpoints

Aim 1: To determine the safety and feasibility of the use of tranexamic acid in pediatric patients receiving chemotherapy or blood and/or marrow transplantation (BMT)

Endpoint: Incidence of adverse events, serious adverse events and death attributed to study drug; Number of patients screened eligible for enrollment and the rate of recruitment during study period

Aim 2: To evaluate the effectiveness of current dose of tranexamic acid for suppressing *in vitro* fibrinolysis

Endpoint: Measures of fibrinolytic activity at baseline (prior to tranexamic acid infusion) and at steady-state

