5.2 Randomization

This trial is designed as a prospective, randomized, controlled, blinded (patient, caregiver, physician, assessor) trial with two parallel groups and a primary endpoint of feasibility and safety. Randomization will be performed as block randomization with a 1:1 allocation within blocks of size four.

When a consented participant's platelet count falls to $\leq 50,000/\mu\text{L}$ and the platelet count is expected to continue to fall and remain $\leq 20,000/\mu\text{L}$ for 5 days or longer, the patient will be randomized to either the tranexamic acid arm or the placebo arm by the investigational pharmacy. When the randomized subject's platelet count is $\leq 30,000/\mu\text{L}$ with an expectation that the platelet count will be $\leq 20,000/\mu\text{L}$ for 5 days or longer the study drug will be activated. Activation of the study drug will act as time point zero for all study endpoints.

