6.3 Stopping Points

The patient's physician or the principal investigator may withdraw the patient from the study for any reason. An End of Study form will be completed with the reason for withdrawal documented in such an occurrence.

The study drug will be permanently discontinued in one of the following circumstances:

- The participant meets an exclusion criteria (either newly developed or not recognized previously) that precludes further study participation
- The patient has been on study drug or received placebo medication for 30 days from the date of study drug activation
- The patient's platelet count increases spontaneously from $<30,000/\mu\text{L}$ to $\geq 50,000/\mu\text{L}$ across two successive platelet measurements with no intervening platelet transfusion
- The patient's platelet count remains $\geq 30,000/\mu\text{L}$ on 2 measurements made at least 46 hours apart without intervening platelet count of $<30,000/\mu\text{L}$ or a decrease in platelet of greater than 50% between two measurements and without intervening platelet transfusion
- The patient is prescribed any other procoagulant, antiplatelet or anticoagulant agent by their treating physician (this includes open label tranexamic acid)
- The patient is discharged from hospital admission
- The patient experiences a thrombotic event
- The patient develops sinusoidal obstructive disease
- The patient develops visible hematuria, renal dysfunction (as defined in Section 6, table 2) or anuria
- The patient has a recurrent incident of complete central line occlusion: defined as the inability to access or infuse through a central line requiring instillation of fibrinolytic agent such as alteplase for clearing. This does not include lines that require certain patient positioning for instillation of agents, which suggest a "kink" in the line. A recurrent incident is when the definition is met on 2 separate occasions while receiving study drug.
- The patient becomes pregnant

If any of the above reasons lead to cessation of the study drug it should not be restarted even if the patient later meets criteria again for the study drug.

Subjects have the right to withdraw consent at any time. If a patient withdraws their consent for further participation, the subject will be asked to grant consent for the study

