8.5 Days 2-30 of Study Drug

- Hemostatic/Bleeding Assessment
- Thrombotic Assessment (via chart review)
- Laboratory Assessment
 - CBC – to be drawn daily
 - Serum Creatinine – to be drawn daily
 - Bilirubin level – to be drawn once weekly
 - Fibrinolysis labs – to be drawn on Day 5 (+/- 1 day)
- Data on Platelet Transfusions
 - Number of platelets transfused
 - Source of platelet transfusions (apheresis or whole blood)
 - HLA or cross-match compatible
 - Reason for transfusion
- Data on Red Blood Cell Transfusions
 - Number of units transfused
 - Reason for transfusion
- Adverse Event Assessment and Reporting - All Grade 3 or greater adverse events will be documented and followed
- Medication Review – Document new or discontinued medications

8.6 Day 7 (+/- 3 days) and Day 30 (+/- 3 days) following Discontinuation of Study Drug

- Hemostatic/Bleeding Assessment (via phone conversation or clinic visit for patients who have been discharged; via chart review for patients who remain inpatient)
- Thrombotic Assessment (via phone conversation or clinic visit for patients who have been discharged; via chart review for patients who remain inpatient)

- Adverse Event Assessment and Reporting (via phone conversation or clinic visit for patients who have been discharged; via chart review for patients who remain inpatient). All Grade 3 or greater adverse events will be documented and followed

Table 3. Timeline for Study Assessment

Schedule of Events	Pre-Treatment Period					Treatment Period		Post-Treatment Period
	Pre-Screening	Day of Enrollment ₁	Days Between Enrollment and Randomization	Day of Randomization ₁	Days Between Randomization and Activation	Day 1 of Study Drug	Days 2-30 of Study Drug	
Event								Day 7 (+/- 3 days) and Day 30 (+/- 3 days) after Discontinuation of Study Drug
Medical Chart Review	X							
Informed Consent		X						
Demographics and Medical History		X						
ABO Type		X						
HLA Testing*		X						
Fibrinolysis Labs						X	X ₂	
CBC		X	X	X	X	X	X	
Serum Creatinine		X		X		X	X	
Urinalysis				X ₃		X ₃		
Coagulation Profile (PT/PTT/INR /Fibrinogen/ D-dimer)		X ₄		X				

Pregnancy Test		X ₅		X ₅				
Bilirubin level							X ₆	
Bleeding Assessment				X		X	X	X
Thrombotic Assessment		X	X ₇	X	X ₇	X	X	X
Data on Transfusion				X		X	X	
Drug or Placebo Administered						X	X	
Adverse Event Assessment						ongoing		
Medication Review	ongoing							

1. Lab studies obtained within 24H period prior to enrollment or randomization do not need to be repeated

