8.7 Fibrinolysis labs

Blood samples will be collected at two time points during the study period to assess suppression of fibrinolysis with study dose of tranexamic acid. At time point one, blood will be collected prior to first dose of study drug to measure baseline fibrinolytic activity. At time point two, blood will be collected at one time point on Day 4-6 of treatment, at least six hours after last dose of study drug and prior to next dose of study drug, in order to assess the suppression of fibrinolysis when tranexamic acid is present at steady state. Samples should be processed and frozen within 4-8 hours of collection. Samples will be stored at the Children's Hospital of Pittsburgh. They will be batched together and shipped to UNC Chapel Hill where fibrinolysis assays will be completed in such a way as to allow for minimum shipments. A portion of each patient's frozen sample will remain at the Children's Hospital of Pittsburgh for use in later biomarker assays of fibrinolysis (unless only minimum quantity required by UNC Chapel Hill has been drawn, in which case all of the sample will be shipped.) At UNC Chapel Hill samples will be

stored until fibrinolysis assays have been completed and then will be disposed of. Samples at the Children’s Hospital of Pittsburgh will be stored indefinitely and used until exhausted. Study participants can request in writing that that samples no longer be used for research and any samples will be destroyed. Study sample may be used at later point for additional testing of the effects of tranexamic acid.

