10.3 Hospital Discharge

Patients discharged from the hospital within 30 days of activation of the study drug will receive their assigned study drug up until the day of discharge. The day of discharge will be the final day of therapy with the study drug. They will be contacted at 7 days (+/- 3 days) and 30 days (+/- 3 days) post cessation of the study drug. These visits may take place in the outpatient clinic (if coinciding with a regularly scheduled return appointment) or by telephone. During these visits patients will be asked for any bleeding or thrombotic events since study drug cessation.

11. Statistical Considerations and Analysis

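### Section 4.1 requires the short predicted stay (≤3 days) that the Section 1 summary excludes, so no patient can meet both eligibility lists

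*Combined protocol and SAP*

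**What the plan says.** Section 4.1, whose criteria must all be met at randomization, includes: "Patients will only be eligible to receive study drug or placebo during a predicted inpatient stay of ≤ 3 days". The exclusion list in the Section 1 summary table, none of which may be present, includes: "Receiving outpatient therapy or predicted to have inpatient hospital stay ≤3 days". Section 4.2, the full exclusion list, does not mention length of stay.

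Four other provisions bear on the point:

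- Section 5.2 randomizes at a platelet count of ≤50,000/uL and activates study drug at ≤30,000/uL, so activation can follow randomization. It adds: "Activation of the study drug will act as time point zero for all study endpoints".
- Section 6.3 gives as a permanent stopping point: "The patient is discharged from hospital admission". Drug stopped for such a reason is not restarted. Section 10.3 adds: "The day of discharge will be the final day of therapy with the study drug".
- For the second fibrinolysis sample, Section 8.7 says "blood will be collected at one time point on Day 4-6 of treatment". Section 8.5 and Table 3 give the same window as Day 5 plus or minus one day. Section 11.5 analyses suppression of fibrinolysis as matched pairs.
- One of the primary endpoints in Section 3.1 is: "Number of patients screened eligible for enrollment and the rate of recruitment during study period".

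**The concern.** The stay that Section 4.1 requires is the stay that the summary forbids. A screener who applies both lists finds nobody eligible. A screener who applies one of them gets a population that does not overlap with the population from the other.

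Two endpoints listed as primary are exposed:

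- **Feasibility.** The number of eligible patients is an endpoint in Sections 3.1 and 11.1.1, and Section 11.7 uses the recruitment results to plan future trials. Contradictory criteria do not define that count.
- **Fibrinolysis suppression.** Each pair needs a baseline sample and a Day 4-6 sample. Section 4.1 taken alone selects patients expected to leave hospital, and so to stop drug, before that window or on its first day. (The Section 1 summary and Sections 3.1 and 11.1.1 treat this endpoint as primary; the synopsis objectives and Section 2 call it secondary.)

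There is also a smaller gap. The plan does not say from which date the predicted stay is counted, or whether it is counted in calendar days or nights.

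**Working it through.** The plan states no figure that depends on this criterion, so there is nothing to reproduce. The check is one of logic and day counting.

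**1. Do the two lists overlap?** Let L be the predicted stay in days. Section 4.1 requires L ≤ 3. The summary requires that L ≤ 3 not hold, that is L > 3. No value of L meets both.

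**2. Could different assessment times rescue the text?** Section 4.1 is judged at randomization and the summary gives no time point, so a patient might move from one range to the other. But Section 6.3 also permanently stops study drug when an exclusion criterion that precludes participation newly develops. Timing is therefore not a dependable way out.

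**3. When does treatment end under Section 4.1 alone?** Let d be the number of days from admission to activation. Activation is Day 1 and the day of discharge is the last drug day (Section 10.3). If the stay runs exactly as predicted:

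- stay counted in calendar days: last drug day = L − d
- stay counted in nights: last drug day = L − d + 1

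With L = 3, the longest stay that Section 4.1 admits:

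| Activation lag d | Calendar days | Nights | Day 4-6 window reached? |
|---|---|---|---|
| 0 | Day 3 | Day 4 | Day 4 only, counting nights |
| 1 | Day 2 | Day 3 | No |
| 2 | Day 1 | Day 2 | No |

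Day 4 is reached in one of these six cases and the nominal Day 5 in none. The six cases are a grid of possibilities, not a frequency. A predicted stay of 1 or 2 days never reaches the window. Even the single Day 4 case works only if the sample is drawn before discharge, at least six hours after one dose and before the next (Section 8.7).

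**4. What if only the sign is corrected?** The shortest whole-day stay above 3 days is L = 4:

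| Stay counted from | Lag d | Calendar days | Nights |
|---|---|---|---|
| Activation | 0 by definition | Day 4 | Day 5 |
| Admission | 0 | Day 4 | Day 5 |
| Admission | 1 | Day 3 | Day 4 |
| Admission | 2 | Day 2 | Day 3 |

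Counted from activation, the shortest eligible stay always reaches the window. Counted from admission, it misses Day 4 once activation lags by one day (calendar days) or two days (nights).

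**The case against.** The strongest reply is that this is an evident slip that staff would read correctly. Much of the plan supports that: the summary exclusion, the Days 2-30 schedule, the Day 5 sample, the 30-day maximum in Section 6.3, and predicted thrombocytopenia of at least 5 days, which is also the starting point for daily screening in Section 5.1. The screening checklist is not among the documents and may already carry the intended rule. On this view the loss of samples follows from a literal reading and is not an expected loss. That is fair, and the figures above should be read that way.

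A second reply is that the sign may have been misread when the text was extracted from PDF. This cannot be fully excluded, but the same list shows ≥ for the lower age limit and for the 5-day thrombocytopenia criterion. If the source does read ≥3, the conflict shrinks but remains: a stay of exactly 3 days would be admitted by Section 4.1 and excluded by the summary.

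A third reply is that the start date of the stay is a clarification and not part of the contradiction. That is correct. It belongs in the same amendment because, as step 4 shows, correcting the sign alone does not guarantee a sample.

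None of this removes the core point. Section 4.1 is the full statement of the inclusion criteria, and as written every patient predicted to stay longer than 3 days violates it.

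**Conclusion.** The concern holds and must be fixed. Applied together, the two lists admit no patients. Under Section 4.1 alone, a 3-day stay ends treatment on Day 3, or on Day 4 at best. Of the 20 planned activated subjects (10 per arm), the only ones who could supply a Day 4-6 sample would be those with a full 3-night stay activated on the day of admission; counted in calendar days there would be none.

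The contradiction needs no assumption beyond the printed signs. The loss of samples rests on two: that Section 4.1 is followed as printed, and that stays run exactly as predicted. A patient who stays longer than predicted would remain on drug and could still be sampled, so the actual loss depends on how accurate the predictions are, and the documents give no data on that. The eligible count is ambiguous from the text; what would actually be counted depends on the checklist in use.

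**What to change.** Reconcile the Section 1 summary with Sections 4.1 and 4.2:

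1. In Section 4.1, make the criterion the complement of the summary exclusion: a predicted inpatient stay of more than 3 days.
2. Add the summary's length-of-stay exclusion to Section 4.2.
3. State the date from which the predicted stay is counted and whether days or nights are meant. Counting from activation places the end of the shortest eligible stay inside the Day 4-6 window under either convention. It does require a forecast of the activation date if the criterion is judged at randomization, so the amendment should also say when it is assessed.
4. Check that the screening eligibility checklist described in Section 5.1 carries the same rule.

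The cost is a protocol amendment with one corrected line, one added line and a short definition, plus the checklist check. The sample size, the schedule and the planned analyses do not change.

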4.2 Exclusion Criteria

To be eligible for participation in the study, potential subjects must not meet any of the following criteria:

- Diagnosis of acute promyelocytic leukemia
- History of ITP, TTP or HUS
- History of inherited or acquired bleeding disorder
- History of inherited or acquired prothrombotic disorder
- Diagnosis of DIC
- Patient must not have WHO Grade 2 bleeding or greater within 48 hours prior to enrollment or study drug activation
- Patient must not have received PEG-Asparaginase within the 7 day period prior to enrollment. If this product is given within the 8-14 day period prior to enrollment patients are eligible if PT, PTT, INR and fibrinogen are obtained and are within 1.5 times the upper limits of normal.
- Patient must not be receiving tranexamic acid or other anti-fibrinolytic agent or any other agent to promote hemostasis (which includes DDAVP, recombinant Factor VII, Prothrombin Complex Concentrate, Estrogen Derivatives and Progestins)
- Patient must not be receiving therapy with anticoagulation or antiplatelet therapy (which includes heparin infusion, enoxaparin, aspirin. If anticoagulant/antiplatelet therapy is discontinued when platelet count is <50,000/uL patient will be eligible for enrollment)
- Patient must not be receiving platelet growth factors
- Patient has a current/prior history of thromboembolic event within the past six months. If history of thromboembolic event the patient should be >30 days from completion of anticoagulation therapy
- Patient has a current/prior history of sinusoidal obstruction disease
- Patient has visible blood in their urine
- Patient with renal dysfunction (defined in Section 6, Table 2), hemodialysis or with anuria (defined as <10mL urine/hour over 24 hours)
- History of seizures
- Allergy to tranexamic acid
- Pregnancy
- Unwilling to accept blood transfusions
- Requires platelet transfusion threshold higher than study protocol (If the patient is enrolled on study and begins treatment with either the study drug or placebo, and subsequently requires a platelet transfusion threshold greater than the study protocol they will remain on study).

5. Trial Enrollment

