11.3 Analysis Populations

Participants will be analyzed according to the groups to which they were initially randomized: tranexamic acid or placebo. All efficacy analysis will be by an Intent to Treat strategy. Participants will be included in the analysis if they received one or more dose of the study drug, even if participant discontinued participation, cross over between treatment groups or received prophylactic transfusions at a threshold higher than that prescribed in the protocol.

Efficacy analysis on patients will include data gathered on patients from the time of activation of the study drug until discharge or until a point 30 days following activation of the study drug, whichever time point occurs sooner. Any participants who have been consented to participate within the study and randomized to a treatment group but did not meet criteria to begin treatment with the study drug (whether due to development of

exclusion criteria or due to platelet count remaining >30,000/uL) and did not receive any doses of the study drug will not be included in the efficacy analysis.

The population of patients used for analysis of safety will be all patients who receive one or more dose of the study drug. Follow-up for mortality and for thrombotic events will occur at 7 days (+/- 3 days) and 30 days (+/- 3 days) post activation. Adverse events and Serious Adverse events will be based on clinical diagnosis obtained from review of the medical record and by patient report during the surveillance period. Patients will be assessed by daily visits and medical chart reviews by the investigator or study staff during the study period. Patients will be assessed by in-hospital visit (if in patient), clinic visit or telephone (if outpatient) during follow-up period after cessation of the study drug.

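### The asparaginase washout is not re-applied at study drug activation, so a dose given between randomization and activation does not, as worded, bar the first dose of study drug

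*Combined protocol and SAP*

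**What the plan says.** Section 4.2 fixes the PEG-asparaginase exclusion to enrollment: "Patient must not have received PEG-Asparaginase within the 7 day period prior to enrollment". The exception that follows, for PEG given 8-14 days earlier with PT, PTT, INR and fibrinogen within 1.5 times the upper limit of normal, is also counted back from enrollment.

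Section 4.1 opens with "Patients eligible for trial must comply with all of the following at the time of randomization" and lists "Patients must be >14 days beyond their last dose of PEG-Asparaginase or >72 hours beyond their last dose of Erwinia Asparaginase", subject to exceptions given later. Erwinia has no entry in 4.2, so its 72-hour washout is an inclusion criterion only.

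Under 5.2 a consented patient is randomized at a platelet count of 50,000/uL or less. Study drug is activated at 30,000/uL or less, given the expected course of the count.

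The bleeding bullet in 4.2 does name activation: "Patient must not have WHO Grade 2 bleeding or greater within 48 hours prior to enrollment or study drug activation". The Section 1 summary matches it ("WHO Grade 2 or greater bleeding within 48 hours prior to enrollment or study drug activation"). Section 8.4 puts it into practice by holding the first dose and allowing activation later.

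Two general provisions bear on the point. Section 6.3 permanently stops study drug when "The participant meets an exclusion criteria (either newly developed or not recognized previously) that precludes further study participation". Section 11.3 deals with randomized patients who never start, among them those who newly meet "exclusion criteria or due to platelet count remaining >30,000/uL) and did not receive any doses of the study drug will not be included". That rule concerns the efficacy analysis.

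**The concern.** The protocol treats recent asparaginase as a reason to keep a child out of the trial, or to admit the child only with acceptable coagulation results. The exposure this precedes starts at activation, not at enrollment or randomization. If asparaginase is given after randomization and before activation, staff who follow the text would start study drug in a child who does not meet the protocol's own washout on that day. Staff who judged this wrong would have no rule telling them whether to dose, wait or withdraw the patient. The drafters tied the neighbouring bleeding criterion to activation, so the difference looks like an oversight rather than a choice.

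**Working it through.** No arithmetic is reported in the plan on this point, so the check sets the rules side by side. Let E, R and A be the times of enrollment, randomization and activation, with E ≤ R ≤ A, and let d be the time of the asparaginase dose.

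| Rule | Source | Counted from |
|---|---|---|
| PEG not within 7 days | 4.2; Section 1 summary | E |
| PEG at 8-14 days, with coagulation limits | 4.2 | E |
| Coagulation tests if PEG or Erwinia given more than 7 and up to 14 days earlier | 8.1; Table 3, footnote 4 | E |
| PEG more than 14 days, Erwinia more than 72 hours | 4.1 | R |
| The same washout | Section 1 summary | not stated |
| No Grade 2 or higher bleeding within 48 hours | 4.2; Section 1 summary; 8.4 | 4.2 and the summary name E or A; 8.4 names A |

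**1. Doses before randomization are covered.**
- A patient who meets the PEG rule at R has A − d ≥ R − d > 14 days.
- A patient admitted under the exception has A − d ≥ E − d ≥ 8 days, with coagulation results in hand.
- For Erwinia, A − d ≥ R − d > 72 hours.
- PEG given between E and R must be more than 14 days old at R, because the exception covers only doses before enrollment.

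**2. Doses with R < d < A are not covered.**
- 4.1 was met at R, before the dose existed.
- 4.2 needs d before E, but d > R ≥ E, so a PEG dose in this interval can never meet the exclusion.
- 5.2 asks only about platelets, and the only hold written into 8.4 is for bleeding.
- The gap A − d can therefore be anything up to A − R. Unless that interval exceeds 7 days, every PEG dose in it falls 7 days or less before the first dose of study drug.

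**3. The interval is foreseen.** Section 8.2 and Table 3 give it its own schedule, including a weekly thrombotic assessment, and 8.4 can lengthen it when bleeding defers activation. It can also be empty, because the introduction to Section 8 allows study points to fall on the same day.

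**4. The general provisions do not reach the dose as worded.** Sections 6.3 and 11.3 both depend on an exclusion criterion being met. By step 2 the PEG exclusion cannot be, and the Erwinia washout is not an exclusion. Ceasing to satisfy an inclusion criterion after randomization is not listed in 6.3. If 6.3 were applied by intent it would also give the wrong remedy, since it forbids restarting, whereas a washout calls for waiting.

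**5. No scheduled clinical coagulation result follows the dose.** The last scheduled profile is at randomization (8.3). The Day 1 list in 8.4 has CBC, creatinine, urinalysis and fibrinolysis samples. Under 8.7 the fibrinolysis samples are frozen and batched for a research laboratory, so they cannot inform the decision to start.

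**6. Frequency cannot be calculated.** The documents give neither the length of the interval nor the number of patients who would receive asparaginase in it.

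**The case against.** The strongest reply is that the protocol's intent is clear and that other safeguards narrow the risk. Sections 6.3 and 11.3 expect newly arising exclusions to stop or prevent dosing. Between randomization and activation, 8.2 requires staff to record new medications and to watch for toxicities of anticancer treatment that would rule out starting study drug. DIC and acquired bleeding or prothrombotic disorders are exclusions with no enrollment date attached, so a clinically evident coagulopathy after an interval dose could be caught. The treating physician or principal investigator may also withdraw a patient for any reason. All of this stands and is why the point is minor. None of it is a rule about asparaginase, though, and a child with a recent dose and no evident coagulopathy would pass.

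A second reply is that 6.3 lists no stop for asparaginase given during the up to 30 days of study drug, so the washout may be meant only as a baseline selection rule. The documents cannot settle this, because they give no reason for the washout. Even as a baseline rule it would most naturally apply at activation, which 5.2 makes time zero for all study endpoints. Repairing the baseline rule leaves asparaginase during treatment as a separate question.

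A reader might infer that the plan leaves these children unprotected, or exposes them to a known interaction. The documents support neither. The partial safeguards above exist, and asparaginase is not among the interacting drugs in 9.4.1 and 9.4.2. Nor should Erwinia be described as having a washout at enrollment: at that point it appears only in the coagulation-testing instruction.

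**Conclusion.** The point holds as a minor, inexpensive improvement. Both asparaginase criteria are anchored before activation, neither is repeated at activation, and the general provisions fall short on their wording. The gap is confined to doses given between randomization and activation.

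This rests on three readings: that the 4.1 criteria apply at randomization, as that section's opening says; that the exceptions 4.1 mentions are the 8-14 day PEG exception in 4.2; and that 6.3 and 11.3 are taken as worded rather than by intent.

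Its importance comes from the protocol's own criterion. How often such a dose would be given is unknown, and no size of harm is claimed. It would be tempting to conclude that the safety comparison or the feasibility result is compromised. Nothing in the documents supports that, and no sample-size or error-rate figure is affected.

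**What to change.** Add study drug activation as a reference point for the asparaginase criteria in 4.1 and 4.2, with matching wording in the Section 1 summary:

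- PEG-asparaginase more than 14 days before activation, or 8-14 days before with PT, PTT, INR and fibrinogen meeting the existing 4.2 limits.
- Erwinia asparaginase more than 72 hours before activation, with no new Erwinia rule at enrollment.

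Add one line to the Day 1 list in 8.4 so that the existing medication review is used to make this check before the first dose. If the washout is not met, defer activation until it is, as 8.4 does for bleeding, rather than stopping permanently under 6.3.

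The cost is amendment wording, a checklist line, and a 2-4 mL coagulation tube (Table 4) only for patients 8-14 days after PEG. Some randomized patients may start late. One who is never activated leaves the efficacy analysis under 11.3 and has to be replaced to reach the 20 activated subjects in 5.3.
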